of death. There is currently no cure or approved treatment for AF. The disease is caused by mutations in the FXN gene (by frataxin). Most patients have repeats of GAA triplets in the first intron of the gene, which leads to lower expression of frataxin. The function of frataxin and the consequences of its deficiency on cellular functions are not fully understood. It has been shown that frataxin is located in the mitochondria where it participates in cellular iron homeostasis, one of the consequences of the lack of frataxin being the deficiency of enzymes with iron-sulfur centers. Alterations in mitochondrial oxidative phosphorylation (OXPHOS) have also been observed in several biological models of frataxin deficiency.

In recent years, cellular models of FA have been used to analyze the ability of various drugs to reverse the consequences of frataxin deficiency. In this sense, we have observed that the active form of vitamin D (calcitriol) is able to significantly improve various phenotypes caused by FXN deficiency in cardiomyocytes and dorsal root ganglia neurons (DRGs). Moreover, calcitriol synthesis may be compromised in AF, as frataxin-deficient cells have decreased levels of CYP27B1 and Fdx1, two proteins necessary for calcitriol synthesis. This synthesis is a mitochondrial process in which the precursor form, 25-OH-vitamin D (or calcidiol), is transformed into 1,25-OH-vitamin D (calcitriol) thanks to the action of CYP27B1. This enzyme has mitochondrial localization and its activity requires the contribution of electrons by ferredoxin 1 (FDX1), a protein containing an iron/sulfur center. Calcitriol synthesis takes place primarily in the kidney, but there is evidence that calcitriol can be synthesized locally in many other tissues, including the brain. In addition, previous studies also indicate that calcitriol may increase mature frataxin levels in various cell types, including frataxin-deficient DRG neurons and lymphoblastoid cell lines derived from patients with FA (Britti et al. see Addendum 1). All these data lead us to consider that calcitriol could be an effective therapeutic agent for the treatment of FA.

There is currently no effective treatment to correct frataxin deficiency in PA, so a drug that has the ability to increase frataxin production to levels at least similar to those of heterozygotes (healthy carriers) could correct or reduce neurological and cardiological deficits in this disease. (Britti et al., Calcitriol increases frataxin levels and restores altered markers in cell models of Friedreich Ataxia. Under revision in "Cell Death & Disease").

Several investigations have at some point obtained an increase in the production of frataxin with other drugs (eg: EPO, nicotinamide, interferon gamma, resveratrol or rosuvastatin). These products achieved smaller increases in frataxin production in the laboratory than those achieved with calcitriol. Although most of them have been followed by the corresponding trials, none of them have provided results that show a significant effect on the clinical situation of patients. Others are ongoing as a study with etravirine (a drug that increases frataxin production by 50%), or are repeated with modifications due to adverse effects or ineffectiveness (nicotinamide, resveratrol).

1.3 Summary of known and potential risks and benefits.

Calcitriol is a drug on which there is vast experience, it has been used for decades in all diseases related to inability of renal synthesis of calcitriol. It has few contraindications: hypersensitivity to the active substance or to any of the excipients included. It should not be administered to patients with hypercalcemia or evidence of vitamin D toxicity. The potential adverse effects are well known (see Addendum 6). Since the most common adverse reaction is hypercalcaemia, successive monitoring of calcium levels will be performed throughout the study and patients will be monitored for symptoms related to hypercalcaemia.

1.4 Description and justification of route of administration, dose, dosage schedule and treatment period.

The ideal dose of calcitriol to raise frataxin levels in patients with Friedreich's ataxia is unknown. Levels of the precursor (25-OH-VitD, known as calcidiol) are below normal in patients with Friedreich's ataxia (Eigentler et al, 2014), but it is not possible to determine calcitriol levels in this research. Therefore, the most prudent option is, in this first study, to use a low dose of calcitriol and check if this is sufficient to raise frataxin levels, in addition to carefully and repeatedly measuring calcemia levels to control possible adverse effects of treatment. This will therefore be the first "in vivo" study in which the possible effect of calcitriol on the production of frataxin in patients with a severe deficit in its production will be analyzed and will allow to know on the one hand the tolerability and safety of the drug in these patients and if a low dose is sufficient to induce changes in neurological function. A single daily dose of 25 micrograms of calcitriol will therefore be used throughout the study treatment period (12 months).

1.5 Description of the population to be studied.

The effects of calcitriol on the neurological function of patients with FA will be studied, among this population will be selected patients who still retain ambulatory capacity, that is, patients who do not yet have a significant degree of disability.

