4.4. Subject withdrawal criteria.

Will be removed from the study:

- to. Any patient who presents hypercalcemia during the controls carried out throughout the trial.
- b. Subjects who present with ECG abnormalities indicative of possible hypercalcemia or arrhythmias during treatment with calcitriol.
- c. Those who repeatedly skip taking treatment.
- d. Those affected who present a new disease or require supplementary treatment that may make the interpretation of the results difficult.

Patients with hypercalcemia and those with ECG abnormalities will continue to be monitored until resolution of symptoms or recorded abnormalities (see Addendum 6).

Telephone or email contact will also be maintained with the patients in section d), although they will not re-enter the study.

Controls with those in section c) will not be followed.

A notification of a serious adverse effect will be made if this occurs (see Addendum 7).

The date of withdrawal from the study and the reason for this, as well as the evolution followed by the patient, will be noted in the CRD.

Subjects who drop out of the study will not be replaced by others as long as the "n" of the study remains between 15 and 20.

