7. SAFETY ASSESSMENT

7.1 Specifying security variables.

- The main safety variable is the determination of corrected calcium levels, measured simultaneously with albumin and proteins at all visits.
- Another variable is the anomalies of the ECG that will be carried out and checked at each visit.
- The deterioration of neurological function at the 6-month visit, or at the time it occurs and can be attributed to the treatment, with no other cause found to justify it (fever, intercurrent illness, etc.).

7.2 Methods and schedule for evaluation, recording and analysis of security parameters.

En el control visitado en 15 days, 4, 8 y 12 months, the following must be evaluated:

- . Calcium, albumin, kidney function, sodium, potassium and phosphate levels.
- . ECG.

The data obtained will be registered in the corresponding CRD.

The normality or not of the corrected calcemia parameters will be assessed.

Hypercalcemia, depending on its severity, can cause increased contractility, arrhythmias, and atrioventricular block. For this reason, the typical ECG abnormalities in hypercalcemia will be especially evaluated: shortening of the QT, especially shortened QTc (defined as the period from the beginning of the QRS to the end of the T wave) and other alterations: increased duration of the wave T (severe hypercalcemia), increased amplitude of the QRS complex, elevation of the ST segment, arrhythmias.

All these parameters will be assessed in each ECG compared with the baseline recording.

7.3 Reporting of adverse events and intercurrent illnesses and registration of adverse reactions.

Adverse events and intercurrent illnesses will be recorded in the corresponding section of the CRD.

Serious adverse events will be especially noted on a separate sheet (Adendum 7).

Each serious adverse event will be reported to the corresponding authorities.

7.4 Type and duration of follow-up after adverse events (AEs).

- Patients with adverse effects will be followed until resolution. If the AE is mild and does not require attention by the researchers, follow-up will be carried out remotely. Otherwise, the patient will be examined at our center in an out-of-program visit.

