9. STATISTICS

9.1 Sample size for a pilot study.

Number of subjects planned: 20

Given the type of study design, a formal calculation of the sample size is not required.

However, general rules for determining the appropriate sample size for a pilot study have been described in the scientific literature. For two-arm studies, it is recommended to recruit between 24-40 patients in total. For single-group studies, the calculation can be adapted by applying an adjustment factor of 0.5. Therefore, in our study it is estimated that it will be necessary to recruit a minimum of between 15-25 patients, assuming a loss rate of 20%.

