9.2 Statistics methods

A descriptive analysis will be carried out using the usual statistics: mean and standard deviation, or median and interquartile range for quantitative variables with non-normal distribution. The normality of the data will be checked using the Shapiro-Wilks test and/or Q-Q plots. The qualitative variables will be described according to the number and percentage of subjects in each category.

The effect of treatment with calcitriol on neurological function will be evaluated using a mixed linear model with the levels of neurological function tests as a dependent variable and the measurement time (screening, 6-month control and final control) as an independent variable included as an effect. random. To take into account possible confounding effects, covariates will be introduced as fixed effects. The same analysis will be repeated for frataxin levels and other biochemical parameters in platelets.

Comparison of baseline frataxin levels between healthy controls and patients with ataxia will be carried out using the Student's t test for independent data or the Mann-Whitney U test, if the data do not meet the assumption of normality. The relationship between the increase in frataxin production and clinical improvement will be

evaluated using a logistic regression model where the dependent variable will be defined dichotomously by jointly evaluating frataxin levels against increases of more than one point on the scale. SARA, two or more points of the SCAFI composite index (which would add the results of the 8 m walk test, time taken from the 9-HPT, the number of syllables from the PATA test), the values of the Barthel Index in 10% and the SF36 questionnaire by 20% on the values obtained in the first evaluation.

The results will be expressed in odds ratio (OR).

The effect of treatment with calcitriol on the quality of life of the patients at the beginning and end of treatment will be evaluated through the t-student test for paired data or the Wilcoxon test, if normality is not met in the distribution of the data.

To assess toxicities, a table of frequencies of occurrences will be created.

Statistical analysis will be performed with o IBM SPSS Statistics version 26 and R software.

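### Section 1.4 expects this pilot to make tolerability and safety known, but discrete toxicities are only tabulated; no events in 20 patients would leave a true risk up to about 17% possible

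*Combined protocol and SAP*

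**What the plan says.** Section 1.4, which justifies the dose and duration, says that the study "will allow to know on the one hand the tolerability and safety of the drug in these patients". The sentence carries no qualification about precision.

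The analysis that answers to it is one sentence in section 9.2: "To assess toxicities, a table of frequencies of occurrences will be created". The general descriptive paragraph of 9.2 adds counts and percentages for qualitative variables, and means or medians with a measure of spread for quantitative ones. No confidence interval, upper limit or acceptable event rate for any safety event appears in the protocol.

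Section 7.1 sets out what is observed: "The main safety variable is the determination of corrected calcium levels, measured simultaneously with albumin and proteins at all visits". ECG abnormalities and attributable neurological deterioration are further safety variables. Section 7.2 classifies corrected calcium as normal or not and compares each ECG with baseline, but names no statistical method for either. The mixed model in 9.2 covers the neurological tests, frataxin and platelet biochemistry, and does not mention serum calcium.

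On size, section 9.1 gives "Number of subjects planned: 20". Section 4.4 does not replace dropouts while the number "of the study remains between 15 and 20". Section 3.2 describes an open pilot in which everyone is treated.

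**The concern.** A frequency table shows what was seen and is silent on what could have been missed. With about 20 patients the second part is large. A row with no arrhythmias or no serious adverse events is compatible with risks that many readers would not call safe, and nothing in the planned output would tell them so.

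This matters in this population. Section 1.2 says that most patients have hypertrophic cardiomyopathy, that the ECG is altered in almost all, and that cardiac dysfunction is the leading cause of death. Section 7.2 names arrhythmias and atrioventricular block among the possible effects of hypercalcemia. These are yes/no events, and they are the kind that a table of 20 patients can miss.

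The denominator is also left open. Section 4.4 withdraws patients for hypercalcemia, ECG abnormalities or repeatedly missed treatment, and stops following the last group. Percentages calculated among completers would describe a selected group.

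**Working it through.** **The plan's own figure.** Section 9.1 starts from a rule of thumb: "For two-arm studies, it is recommended to recruit between 24-40 patients in total". It continues: "For single-group studies, the calculation can be adapted by applying an adjustment factor of 0.5". It then allows for 20% loss.

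- Lower end: 24 × 0.5 = 12, and 12 / (1 − 0.20) = 15.
- Upper end: 40 × 0.5 = 20, and 20 / (1 − 0.20) = 25.

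This reproduces the stated range of 15 to 25, and the planned 20 lies inside it. The number comes from a general pilot rule; no safety event rate enters it.

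**Inputs for the safety check.** n = 20 (section 9.1) and 12 months of treatment (section 1.4). The documents give no confidence level, so 95% is assumed and shown both two-sided and one-sided. They also give no risk of interest, so the risks below are illustrative.

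**Upper limit after zero events.** The exact (Clopper-Pearson) limit solves (1 − p)^n = α, which gives p = 1 − α^(1/n), with α = 0.025 for a two-sided and 0.05 for a one-sided 95% limit.

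- Two-sided, n = 20: 1 − 0.025^(1/20) = 16.8%.
- One-sided, n = 20: 1 − 0.05^(1/20) = 13.9%.

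If all 20 start treatment, the all-dosed denominator is 20. Should fewer be available, the limits widen:

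| n | Source | Two-sided | One-sided |
|---|---|---|---|
| 20 | planned number | 16.8% | 13.9% |
| 16 | 20 × (1 − 0.20) | 20.6% | 17.1% |
| 15 | floor in section 4.4 | 21.8% | 18.1% |

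**Chance of an empty row.** P(no events) = (1 − p)^n with n = 20:

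- p = 10%: 0.90^20 = 12%.
- p = 5%: 0.95^20 = 36%.
- p = 2%: 0.98^20 = 67%.
- p = 1%: 0.99^20 = 82%.

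An empty row is the more likely result only when p is below 1 − 0.5^(1/20) = 3.4%.

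**Rows with events are imprecise too.** The exact two-sided 95% interval is 0.1% to 24.9% for 1 of 20, and 1.2% to 31.7% for 2 of 20.

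**The case against.** The strongest reply is that this is a declared pilot, that descriptive tabulation of adverse events is ordinary at this size, and that any reader can work out the zero-event bound from n. Sections 1 and 1.3 also rest tolerability on decades of use of calcitriol. Pilot status does support modest wording. Section 1.4, however, is not modest, and it speaks of safety in these patients specifically. A pilot can report an interval as easily as a percentage.

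Several stronger readings are tempting, and the documents do not support them.

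- *That the plan will declare the drug safe if no events occur.* Section 1.4 says only that safety and tolerability will become known. No safety success criterion or no-event rule exists.
- *That larger trials or continued treatment would rest on an empty toxicity table.* Section 1 links positive results to an effective treatment, and section 3.4 links continuation to the comparison of neurological function. Neither mentions the table.
- *That safety assessment amounts to one bare table.* Sections 7.1 and 7.2 plan repeated calcium measurements and ECGs compared with baseline, and 9.2 would summarise calcium as a quantitative variable. The gap is confined to yes/no events.
- *That seeing no events is the likely outcome even at a relevant risk.* This is true only below about 3.4%. At 5%, at least one event is more likely than none (64% against 36%).

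**Conclusion.** The point stands as a limit on what the safety data can support. Section 1.4 claims more than a frequency table in 20 uncontrolled patients can deliver: with no events, a true risk of up to 16.8% (two-sided 95%) remains compatible with the data, and a 5% risk would go unseen about one time in three.

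This rests on all 20 patients taking at least one dose, on independent patients with a common risk, and on the assumed 95% level. Reading the figures as one-year risks further requires follow-up of everyone for the full year; early withdrawal would make them less informative. The 5% and 2% risks are illustrations only.

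The change should be made, because it alters what the trial may conclude about safety. It does not expose an error in any planned decision, and it leaves the estimation of calcium as a continuous measure untouched.

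**What to change.** In section 9.2, state that each discrete toxicity (hypercalcemia, ECG abnormality or arrhythmia, serious adverse event, other adverse event) will be reported as patients affected over all patients who took at least one dose, with a two-sided exact (Clopper-Pearson) 95% confidence interval. Include rows with zero events. Naming the sidedness matters, since a bare reference to an upper 95% limit could be reported as either 13.9% or 16.8%.

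In section 1.4, say that the study will give preliminary data on safety and tolerability, and that no events in 20 patients would still be compatible with a true risk of up to about 17%.

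The cost is one column in a table already planned and one reworded sentence, with no extra patients, visits or measurements. The downside is that the stated safety conclusion becomes less favourable.

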a) This study also aims to control the effects that said drug may have on the calcium level of the monitored individuals. Calcitriol supplementation is considered safe since the recommended doses are well known. However, it is necessary to control the effects that such supplementation may have on the calcium level of Friedreich's ataxia patients.

b) Analyze the effect of calcitriol administration on frataxin levels and other biochemical parameters in platelets obtained from the patients under study. Frataxin is undetectable in serum or plasma, while its detection in blood is not recommended for the objectives of the project, since it is present in erythrocytes which have a high half-life (around 115 days). This could make it difficult to observe changes in frataxin content due to the treatments carried out. Therefore, its platelet content will be analyzed, since these have a half-life of 10 days. Platelets can be easily obtained from

circulating blood and contain active mitochondria that sustain most of their ATP production. Various mitochondrial proteins will also be quantified throughout the study and the effect of calcitriol on their production.

c) Effect of treatment with calcitriol on activities of daily living with the Barthel Index and quality of life using the SF36 questionnaire, at the beginning and at the end of treatment.

3. TRIAL DESIGN

Given the purpose of the trial, the neurological function of the patients will be evaluated prior to the start of treatment, at 6 months and at 12 months. The duration is determined by the characteristics of the disease, which is neurodegenerative and therefore changes in neurological function are not expected until after a long period of time. Neurological function will be assessed using standardized tests aimed at assessing cerebellar motor function, gait, dysarthria and manual dexterity. This includes the SARA scale for assessing and grading cerebellar function, the eight-meter walk test (time taken by the patient to travel 8 meters in both directions and calculating round trip and average), a dexterity test, the 9-Hole Peg test (the time spent placing nine pegs in 9 holes, with the dominant and non-dominant hand, is assessed, and the PATA speed test, for assessing dysarthria, in which the number of times is counted that the patient emits these syllables in two periods of 10 seconds, calculating the number in each series and the average of both).

All these tests will be videotaped and the files obtained will be archived on an external hard drive for conservation, evaluation, reproduction and subsequent comparison. In this first visit, measures of activities of daily living will be taken using the Barthel Index and also the SF36 questionnaire (Spanish version of SF-36v2™).

Control visits will be made at 15 days, 4, 8 and 12 months, to check calcium levels (among other analytical determinations), symptoms of adverse effects, and ECG. Communication with patients will be facilitated with various methods (telephone, email) to assist them in any eventuality.

In these same visits and with the same extraction, samples will be obtained to determine frataxin levels. Frataxin will be quantified by western blot of platelet lysate.

In the same lysate, various mitochondrial proteins will be quantified by SRM-based mass spectrometry.

3.1 Specific description of the main and secondary variables.

As primary variables, the parameters obtained from the aforementioned neurological function tests will be specifically evaluated: SARA scale values, time to travel 8 meters, time to complete the 9-hole test, number of syllables of the dysarthria test.

Secondary variables will be evaluated: calcium levels and kidney function, frataxin levels, Barthel index values and SF36 quality of life questionnaire.

3.2 Description of the type of trial.

The present study is a pilot study aimed at verifying the effects of treatment with calcitriol on neurological function, calcium levels, frataxin levels, and quality of life in patients with FA.

This is an open study, all patients will receive treatment, and the results obtained before and after treatment will be compared, using parameterized tests and video filming.

3.3 Description of trial treatment.

The drug used, calcitriol, is on the market under the registered trademark Rocaltrol®. The lowest dose will be used: 25 micrograms, orally once a day for one year (Rocaltrol 0.25 micrograms soft capsules, presented in a PVC blister containing 20 capsules).

3.4 Expected duration of participation and all trial periods.

The study will continue over one year.

It will begin with a recruitment period, a screening period that includes the evaluation of inclusion and exclusion criteria, the assessment of neurological function, a determination of calcium, vitamin D, kidney function, albumin, proteins, sodium, potassium, phosphate, and pregnancy test in pre-menopausal women, and extraction for basal determination of frataxin, evaluation of the quality of life questionnaire. An ECG will also be performed.

The treatment period will begin from here.

Fifteen days after the start of this, the next visit will be carried out with the first extraction for determination of frataxin, calcium, kidney function, sodium, potassium, phosphate, ECG and assessment of possible symptoms related to possible adverse effects of the treatment.

This procedure will be repeated at 4, 8 and 12 months with determination of frataxin, calcium, albumin, kidney function, ECG and assessment of possible symptoms related to possible adverse effects of the treatment (Addendum 6).

After 6 months of treatment, the first assessment of neurological function will be carried out.

At the last visit of the 12 months, a new assessment of neurological function, Barthel index and final quality of life questionnaire will also be carried out (Addendum 5.1, Addendum 5.2, Addendum 5.3 and Addendum 5.4).

Post-study follow-up, the data obtained will be analyzed and its statistical evaluation will be carried out. Patients who wish to continue treatment will be allowed to continue, at least until the first results of the comparison of the initial neurological function with the second and final ones are obtained. If the results obtained are positive, treatment will be maintained in these patients with regular analytical controls. If the result does not demonstrate a statistically significant result, this will be discontinued in all patients. Detection of hypercalcemia will lead to immediate withdrawal from the study.

If possible, patients who show improvement will be followed up in our Ataxia Unit.

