3.5 Prescription and dispensing of treatment. Accounting for study medication

The investigational medication is marketed under the name ROCALTROL 0.25 MCG 20 capsules.

Conservation: at room temperature (20–25°C).

If a patient agrees to participate in the study, the research team will contact the Pharmacy Service to inform of this inclusion.

The Neurology service will prescribe the medication (Calcitriol 0.25 mcg capsules (ROCALTROL®) through a prescription for specially prescribed medications, a model for internal use in the hospital.

Information to be completed by the research team:

- Patient identifying data: patient name and surname, medical record number and assigned patient number
- Prescribing doctor: Name, registered number, signature and date
- Code and/or abbreviated name of the study protocol
- Visit number within the study calendar

The Pharmacy service will dispense to the patient based on said prescription and the period that must be covered until the next study visit (4 months, equivalent to 120-123 days).

The study medication will be properly relabeled in the Pharmacy service as a clinical trial sample. A label will be used for the medication carton with the following information:

Active principle
Pharmaceutical Specialty
Route of administration
Batch and expiration
Name and Number of the patient in the study

and another for the dispensing bag, according to the following model:

STUDY: FA-CALCITRIOL

Promoter: Joint IAS/ICS Neurology Service

Address: [name], [name] Tel. [name]

Researcher: [name] [name]

Patient number

Patient Name.....

_____ packaging ROCALTROL 0.025 mcg 20 Capsules

Store at room temperature.
Protect from sunlight.
KEEP OUT OF THE REACH OF CHILDREN

Sample for clinical research

From the IAS Pharmacy Service, control of the dispensing and return of all dispensed containers will be carried out, counting the medication returned by the patient after

each visit, without prejudice to the fact that said count is also carried out by the research team. , so that there can be a double check on adherence to treatment, by the research team and by the Pharmacy service.

The returned medication will be kept in the Pharmacy service itself, for final counting by the research team. The accounting of medication as well as patient dispensations and returns will be carried out through the Fundanet application.

Expiration control of the study medication will be carried out.

SCHEDULE

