More specifically, patients affected by some other disease that interferes with the patient's assessment, whether medical or neurological, will be excluded. Patients with severe visual or auditory deficits will also be excluded, as well as those with cognitive impairment (dementia or cerebellar cognitive affective syndrome), or mentally or legally incapacitated subjects. Those affected by serious psychiatric illnesses, or those with a history of substance abuse within the 6 months prior to screening, will also not be admitted. Avoid including patients who have suffered severe allergies to medications, those who present heart disease of a certain entity (detailed in Addendum 4.1 and Addendum 4.2) and those who have taken investigational drugs in the 30 days prior to inclusion. Patients under treatment with digoxin, thiazide diuretics, cholestyramine, corticosteroids, laxatives with magnesium, barbiturates and antiepileptics, calcium or vitamin D will also not be accepted for the study.

Pregnant or breastfeeding women will not be admitted.

Patients who meet the inclusion criteria and those in whom no exclusion criteria are detected will be admitted, then the patient will sign the informed consent.

Instructions will be given for the dosage of treatment with the drug calcitriol (Rocaltrol© 0.25mcgs).

The patient will be provided with the schedule of visits and appointments for the entire study.

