5. SUBJECTS TREATMENT

5.1 Trial treatment.

The only treatment in the study is calcitriol (Rocaltrol©) at 0.25 micrograms/day orally.

5.2 Allowed medications.

Patients under treatment with idebenone or coenzyme Q10 for years.

De novo inclusion of idebenone will only be permitted in patients who develop signs of cardiomyopathy during the study.

5.3 Not allowed medications.

They will not be able to enter the study, but patients who require treatment with digoxin, amiodarone or thiazide diuretics, corticosteroids, cholestyramine, magnesium laxatives, barbiturates and antiepileptics, calcium or vitamin D will not be included or withdrawn.

Nor those who continue treatment with other tested drugs other than idebenone, which include: diperiprone, EPO, resveratrol, nicotinamide, etravirine, rosuvastatin, interferon of any type, EPI743 (vatiquinone), CTI-1601, RT001 (stabilized linoleic acid), pioglitazone, lericlitazone (MIN-102), epicatechin, ovameloxolone, VP 20629 (propionic acid), varenicline, ginko biloba, alpha-tocopherol-quinone.

If a patient has followed a treatment in a clinical trial with any of these drugs, they will be allowed to enter the study only after a washout period of 6 months.

Other drugs will be admitted as long as these drugs do not interfere with the assessment of the results or the neurological function of the patients or modify the calcium levels directly or indirectly.

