5.4 Hypercalcemia treatment

The risk of hypercalcemia with Calcitriol 0.25mcg/24h is very low. It increases in patients in situations of prolonged immobilization, treatment with digoxin and thiazide diuretics among others, these patients being already excluded from the study.

The treatment of hypercalcemia will be based on the severity of the hypercalcemia (see Addendum 8):

- Mild hypercalcemia (Calcium 10.2-12mg/dl): withdrawal of treatment, abundant water intake and analytical control after 7 days.
- Asymptomatic moderate hypercalcemia (Calcium 12-14mg/dl): similar to the treatment of mild hypercalcemia, possibility of treatment with Prednisone 20-40mg/24h
- Moderate symptomatic hypercalcemia (Calcium 12-14mg/dl): withdrawal of treatment. Hospital admission for hydration with physiological saline, treatment with Pamidronate (a bisphosphonate), analytical control at 12-24 hours.

- Severe symptomatic hypercalcemia (Calcium >14mg/dl): withdrawal of treatment. Hospital admission for hydration with physiological saline, treatment with Zolendronate (a bisphosphonate), evaluate treatment with subcutaneous Calcitonin and Prednisone, analytical control at 12-24 hours.

5. 5 Procedures to monitor subject compliance. Patient's diary.

At each visit the patient will be given a "Patient's Diary" in which they will be asked to write down the date, check a box if they take the treatment, and write a note if any new symptoms appear or any abnormality occurs related to taking the treatment. The patient will provide this list at each visit (see Addendum 9).

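### The daily calcitriol dose is 25 micrograms in sections 1.4 and 3.3 but 0.25 micrograms in 5.1 and 5.4 (100-fold), and the bag label model prints a capsule strength 10-fold too low

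*Combined protocol and SAP*

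**What the plan says.** Four places in the combined protocol and SAP state a daily dose, and they split two against two.

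- Section 1.4 (dose justification): "A single daily dose of 25 micrograms of calcitriol will therefore be used throughout the study treatment period (12 months".
- Section 3.3 (trial treatment): "The lowest dose will be used: 25 micrograms, orally once a day for one year". The same sentence goes on to name the product: "Rocaltrol 0.25 micrograms soft capsules, presented in a PVC blister containing 20 capsules".
- Section 5.1 (trial treatment): calcitriol "at 0.25 micrograms/day orally".
- Section 5.4 (hypercalcemia): "The risk of hypercalcemia with Calcitriol 0.25mcg/24h is very low".

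Three further places give a capsule strength but no daily dose.

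- Section 3.5, product name: "The investigational medication is marketed under the name ROCALTROL 0.25 MCG 20 capsules". The prescription described in that section is also for 0.25 mcg capsules.
- Section 3.5, model label for the dispensing bag: "packaging ROCALTROL 0.025 mcg 20 Capsules".
- End of section 4.2: "Instructions will be given for the dosage of treatment with the drug calcitriol (Rocaltrol© 0.25mcgs".

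**The concern.** There are two separate errors. The first is the daily dose: the section that justifies it and the section that describes the treatment both give a figure 100 times the one in 5.1 and 5.4. Section 3.3 also conflicts with itself, since a dose presented as the lowest cannot need 100 of the capsules named beside it. The second is the capsule strength on the bag label, which disagrees with the product name and the prescription in the same section.

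These are operative figures that bear on safety. Section 1.3 names hypercalcaemia as the most common adverse reaction, and section 4.4 withdraws any patient who develops it. The reassurance in 5.4 is given for 0.25 micrograms per 24 hours and lends no support to 25. Section 1.4 argues for a cautious, low starting dose and then prints a number that contradicts the argument. The label model is a template, so an error in it would be repeated for every patient.

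**Working it through.** **Inputs**

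- Daily dose: 25 micrograms (1.4, 3.3) or 0.25 micrograms (5.1, 5.4).
- Capsule strength: 0.25 mcg (3.3, 3.5, 4.2) or 0.025 mcg (bag label model, 3.5).
- Pack size: 20 capsules (3.3, 3.5).
- Dispensing period: 120 to 123 days (3.5).
- Treatment: one year, taken as 365 days.

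**Can the stated dose be reproduced?** Daily dose = capsule strength × capsules per day. One 0.25 mcg capsule once a day gives 0.25 × 1 = 0.25 micrograms. That matches 5.1 and 5.4 but does not give the 25 micrograms of 1.4 and 3.3.

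**Ratios**

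- Dose: 25 / 0.25 = 100.
- Label strength: 0.25 / 0.025 = 10.

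**Supply implied by each dose**

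| | 0.25 micrograms/day | 25 micrograms/day |
|---|---|---|
| Capsules per day | 0.25 / 0.25 = 1 | 25 / 0.25 = 100 |
| Capsules per dispensing period | 120 to 123 | 12,000 to 12,300 |
| Packs of 20 per dispensing period | 6.0 to 6.15 (6 or 7 whole packs) | 600 to 615 |
| Capsules per year | 365 | 36,500 |
| Packs of 20 per year | 18.25 (19 whole packs) | 1,825 |

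The right-hand column could not be dispensed or swallowed, so 25 micrograms cannot be what is meant.

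**If someone relied on the bag label.** To reach 0.25 micrograms with capsules believed to hold 0.025 mcg, a reader would count 0.25 / 0.025 = 10 capsules. With the real product that is 10 × 0.25 = 2.5 micrograms, ten times the intended dose. A supply of 120 to 123 capsules would then last 120 / 10 = 12.0 to 123 / 10 = 12.3 days, which ends before the first on-treatment calcium check at 15 days.

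**Is the number of capsules per day stated anywhere?** Not in the text supplied. The items section 3.5 lists for the prescription, the carton label and the bag label do not include it.

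**The case against.** The strongest case against is that the errors largely reveal themselves. The named product and the prescription are 0.25 mcg, nobody could dispense 100 capsules a day, and one capsule follows from section 5.1 combined with the once-daily schedule and the capsule strength. The ten-capsule scenario is also remote: the bag label model carries no dose to divide by, the carton has its own label, patients receive dosing instructions, supply is matched to the visit interval, and returned capsules are counted twice. Patient-facing dose wording may also exist in addenda that are not in the supplied text. Finally, the document is a translation with some Spanish left in it, so a lost leading zero is conceivable.

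Much of this stands as a limit on the likely harm. It is also fair that section 4.2 supports the capsule strength only, and that this is an internal inconsistency, since no calculation in the plan goes wrong. None of it makes the three figures right. The 25 microgram figure is well formed in two separate sections, and section 3.3 prints 0.25 correctly a few words later. The label error takes a different form, an added zero, so one reading or translation fault would not easily explain all three. If translation is the cause, the current text still needs correcting.

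**Conclusion.** The concern holds. The daily dose in sections 1.4 and 3.3 is 100-fold above that in 5.1 and 5.4, the bag label strength is 10-fold below the product, and nothing in the document reconciles them. That 0.25 micrograms a day is intended is an inference from the capsule strength, the low-dose rationale, sections 5.1 and 5.4, and the impossibility of 100 capsules a day. It is a strong inference, but the sponsor should confirm it. The finding does not imply that any patient would receive 25 micrograms. The prescribed strength and the pill counts are unaffected unless someone acts on a wrong figure. Correction is still required, because these are operative figures for the only study drug and the safety statement in 5.4 applies to just one of the two doses.

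**What to change.** After the sponsor confirms the intended dose:

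1. Section 1.4: change 25 micrograms to 0.25 micrograms.
2. Section 3.3: change 25 micrograms to 0.25 micrograms.
3. Section 3.5, dispensing-bag label model: change 0.025 mcg to 0.25 mcg before any dispensing.

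It is also worth stating one 0.25 mcg capsule per day in section 3.3 and on the label. This is an improvement in clarity that goes beyond correcting an error. Sections 4.2, 5.1 and 5.4 need no change.

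The cost is three figures, one optional phrase and a corrected label template. No extra patients, visits or procedures are needed.
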